Aim 2: Determine the effect of these interventions on cortical markers of inhibitory control that are also affected in FM, such as intracortical inhibition as assessed by transcranial magnetic stimulation (TMS) and changes in thalamocortical dysrhythmia as assessed by EEG. *We hypothesize that active tDCS combined with exercise will result in greater increases in intracortical inhibition as measured by the short intracortical inhibition (SICI). These increases will be associated with greater reduction of pain when compared to either intervention alone. We also hypothesize that tDCS combined with exercise will induce a greater decrease in theta power than any intervention alone, as well as to the control group. Therefore, we hypothesize that decreases in theta EEG band power could be used as a marker of the normalization of the thalamic dysrhythmia normalization.*

Aim 3: Assess the number of sessions needed to induce significant changes in markers of endogenous pain inhibitory system and central sensitization (CPM and TSPS) and cortical changes (as indexed by paired pulse TMS and EEG). *We hypothesize that the group receiving the top-down and bottom-up strategies (tDCS and AE) will have a greater number of subjects with target engagement (change of at least 30% as compared to baseline) of pain and cortical marker.*

Sub-aim 3: Assess whether engagement of the two main targets tested in this study – TSPS and CPM – are associated with the secondary clinical outcomes (i.e., changes in pain outcomes: Brief Pain Inventory, Revised Fibromyalgia Impact Questionnaire). *We hypothesize that changes in TSPS and CPM will be correlated with these pain outcomes. We also hypothesize to find a correlation between baseline values of TSPS and CPM and pain relief immediately after the intervention.* This result will be important as to assess the suitability of such markers as potential treatment response predictors.

[figure not shown]
III MEDICAL MONITOR

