The primary analysis: All the analyses will be performed as intention-to-treat in which all subjects undergoing randomization who receive at least one intervention session (randomization will take place immediately before the first intervention) will be included. We will conduct sensitivity analyses and test different models of handling missing data (LOFC and MI). The change in the primary efficacy endpoint, CPM (and also TSPS), from baseline to week 4 will be tested with a mixed linear model. This model will be adjusted for important demographic variables (i.e., gender) and also baseline clinical parameters where appropriate. All tests will be two-sided (alpha level, 0.05). We will initially test our main hypothesis that the combined treatment induces a greater increase in CPM (and decrease in TSPS) as compared to the control condition. If the effect is significant, we will then test differences between the combined group vs these two interventions alone.

[figure not shown]
In order to understand the time effect of this intervention (using the secondary endpoints added in this model (week1 and follow-up)), we will run a secondary mixed linear model to estimate the rate of change over time by also including an interaction between treatment and time as to detect whether treatment effect changes differently according time. If the interaction is not significant we will then test whether there is a main effect of time that is independent of treatment level (interaction will be then removed from the model). We will adjust this model for important covariates such as age, gender, pain levels (numeric pain scale – NPS), and other baseline clinical outcomes where appropriate. For the secondary clinical variables with a significant effect we will also test whether they moderate the interventions' effects on our mechanistic outcomes, thereby gaining additional mechanistic insights.

To complete our analysis, we will apply a path analysis [1, 2] to the outcome data (CPM and TSPS) to determine if endogenous pain modulation changes (as indexed by CPM and TSPS) associated with the combined intervention (tDCS and AE) is related to direct effects versus indirect effects through improvements in secondary outcomes. We propose that a direct effect of tDCS and AE on the endogenous pain inhibitory system can be inferred if the treatment effect cannot be explained by changes in psychological or functional outcomes.

[figure not shown]

[figure not shown]
Detailed Protocol 23

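### Moderators are picked from secondary clinical variables with a significant effect and are not limited to baseline values, so a treatment-affected variable may be tested as a moderator and true modifiers may be screened out

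*Combined protocol and SAP*

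**What the plan says.** The rule stands in section VIII (Planned Analysis), in the paragraph on the secondary mixed model over time: "For the secondary clinical variables with a significant effect we will also test whether they moderate" the treatment effects on the mechanistic outcomes (CPM and TSPS). It gives no list of variables and no time point, and it does not say what the significant effect is an effect of. The only threshold is the general one: "All tests will be two-sided (alpha level, 0.05" (significance level).

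Three other statements bear on its meaning.

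- Section II, Sub-aim 3, describes the "secondary clinical outcomes (i.e., changes in pain outcomes: Brief Pain Inventory, Revised Fibromyalgia Impact Questionnaire". These are changes, so they are known only after treatment has begun.
- The next paragraph of section VIII sets up a path analysis of "direct effects versus indirect effects through improvements in secondary outcomes". There the secondary outcomes act as mediators between treatment and CPM or TSPS.
- The sentence just before the rule reads: "We will adjust this model for important covariates such as age, gender, pain levels (numeric pain scale – NPS), and other baseline clinical outcomes where appropriate". Here the baseline values are adjustment covariates. The word baseline is not carried over to the moderators.

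The outcome whose treatment effect would be moderated is set in the primary analysis: "The change in the primary efficacy endpoint, CPM (and also TSPS), from baseline to week 4 will be tested with a mixed linear model".

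**The concern.** A moderator describes who benefits more or less from treatment, so its value must not itself depend on treatment. A variable that treatment has moved fails that condition. If some patients respond well on both pain and CPM, change in pain will track change in CPM more closely in the treated arm than in the control arm. A treatment by change-in-pain interaction then appears, although no patient characteristic at entry predicts benefit.

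The plan also leaves the same class of variables open to two roles: moderator in one paragraph and mediator in the next.

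The stake is interpretive. The protocol presents this as a mechanistic trial, and the moderation step is justified by the mechanistic insight it should give. A false modifier, or a true one never tested, would mislead on that purpose.

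**Working it through.** **Number per arm.** The plan gives no figure for the moderation analysis, so only the sample size can be reproduced. Inputs from section VIII: effect size 0.90, two-sided alpha 0.05, power 85%, dropout 20%. With the normal approximation, n = 2 × (1.960 + 1.036)² / 0.90² = 22.2, so 23 per arm. Then 23 / 0.80 = 28.75, so 29 per arm, and 4 × 29 = 116, as stated. The check below uses 23 per arm, the number left after dropout, and compares the combined arm with control.

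**Reading 1: a post-treatment change is tested as the moderator.** The following inputs are assumptions; only the 0.90 comes from the plan. T is treatment (0 or 1), u and e are independent standard normal, and R is an individual response with SD λ that is shared by both outcomes. No baseline variable modifies the effect.

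- Change in the clinical variable: M = u + T(0.5 + R)
- Change in CPM: Y = ρu + √(1 − ρ²)e + T(0.90 + R)
- Test: the T × M term in a linear regression of Y on T, M and T × M, two-sided 0.05

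The slope of Y on M is ρ in the control arm and (ρ + λ²)/(1 + λ²) in the treated arm. The built-in difference in slopes is therefore λ²(1 − ρ)/(1 + λ²). It is zero when λ = 0, grows with λ and shrinks as ρ rises. For λ = 1 it is 0.50 at ρ = 0, 0.35 at ρ = 0.3 and 0.25 at ρ = 0.5.

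Simulated share of trials in which T × M is significant:

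| Background correlation ρ | λ = 0.5 | λ = 0.8 | λ = 1.0 |
|---|---|---|---|
| 0 | about 9–10% | about 23–24% | about 36–37% |
| 0.3 | about 7–8% | about 15–16% | about 23–25% |
| 0.5 | about 6–7% | about 12% | about 17–18% |

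Ranges reflect simulation noise between runs. With λ = 0 the rate is about 5%. A baseline variable tested as moderator in the same data is significant in about 5% of trials throughout. At 29 per arm and ρ = 0.3, the post-treatment rates are 8.9% for λ = 0.5 and 29.2% for λ = 1.0.

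**Does the significance filter cause the excess?** No. At ρ = 0.3, λ = 1.0 and 23 per arm, the rate is 23.8% over all trials and 22.5% among trials in which the clinical variable showed a significant treatment effect. The excess comes from using a post-treatment variable.

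**Reading 2: baseline covariates with a significant term.** Take a baseline variable B with a true interaction of 0.8 SD per SD (assumed) and no average main effect: Y = 0.90T + 0.8(T − ½)B + e, with 23 per arm. Tested directly, the interaction is found in 71% of trials. If it is tested only when B has a significant main effect, it is found in 4%.

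**The case against.** The strongest reply is that the moderation sentence directly follows the one on baseline covariates. Read in sequence, the clinical variables with a significant effect could be baseline covariates with a significant term in that model. Sub-aim 3 sits in another section, speaks of outcomes where section VIII speaks of variables, and concerns correlation, not moderation. On this reading no treatment-affected variable is tested. That stands as a possible reading, and the text does not settle it. It does not rescue the rule, because screening on a main effect is still unsuitable.

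A second reply is that the size depends on assumptions. That also stands. The documents give neither the shared-response SD nor the background correlation. Sub-aim 3 expects changes in CPM and TSPS to correlate with the pain outcomes, so zero correlation should not be the only case shown. If patients respond uniformly, the test keeps its 5% level.

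A third reply is that this is one exploratory sentence attached to a secondary model, and that the path analysis already covers the post-treatment pathway. That stands and limits the consequence.

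A reader might infer more: that the plan will name false modifiers, or that selection on significance inflates the error. The documents do not support the first, because it needs one reading of an ambiguous sentence plus a shared response. The check above does not support the second.

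**Conclusion.** The concern holds in a limited form. The rule selects moderators by a significant effect without confining them to baseline values, and it is poor on both readings. On the first, a treatment-affected variable may be tested as a moderator. With 23 per arm and an assumed shared-response SD of 0.5 to 1.0, the false-positive rate runs from about 6% to about 37%, depending on the background correlation, against about 5% for a baseline moderator. On the second, a true modifier without a main effect is nearly always screened out: 4% found against 71%, for an assumed interaction of 0.8 SD per SD. These figures illustrate the mechanism and do not predict this trial's results.

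The primary comparison of CPM and TSPS, the sequence of arm comparisons and the sample size of 116 are untouched. The point deserves a change because the step is meant to support mechanistic claims and the correction is cheap.

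**What to change.** Replace the moderation sentence in section VIII with a rule of this form:

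- Name a short set of clinical variables in advance. The choice is the sponsor's; BPI, FIQ-R and BDI are examples.
- Test the treatment by baseline-value interaction for each, whether or not the variable has a significant effect.
- Label these analyses exploratory and report each interaction estimate with its 95% confidence interval.
- Use post-treatment clinical changes only in the path (mediation) analysis.

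If baseline values were intended all along, one sentence saying so, the named list and removal of the significance condition are enough.

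The cost is a change of SAP wording. No new data are needed: pain and quality of life are assessed at visit 1.1, and FIQ-R and BDI are given at the start of the study. The downside is that a few exploratory interactions will be reported even if they are null.

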Sample Size Calculation: This study's original sample size calculation was based on an expected effect size of 0.78, with 85% statistical power and a significance level of 0.05. However, after 6 years of the original sample size calculation (it was done in 2017 upon grant submission, see appendix 2), we have observed in our recent study in collaboration with other colleagues and recent meta-analyses effect sizes ranging from 0.9 to 1.26, which are larger than we initially anticipated. Considering this new information, we re-estimated the sample size to ensure we do not expose subjects to the burden of participating in a study that involves a placebo arm. Also, this would make the study feasible to be completed in the 5-year period of this grant, given our recruitment was significantly affected by the COVID pandemic, especially in the years 2020 and 2021. We have recalculated the sample size using the smallest reported effect size (0.90) using the t-test calculation for the difference between two independent means (to test for the main hypothesis) – this is the same method used in the original sample size calculation; and determined that we need a total of 116 participants (29 in each group) to achieve 85% power (as planned before). We assumed a type I error of 5% (alpha), and a type 2 error of 15% (beta). We also made this calculation considering the same parameters used in the original sample size calculation, such as dropout rates of 20%. The sensitivity analysis for the sample size calculation is summarized in the table below.

[figure not shown]
Therefore, we reduced the sample size from 148 to 116 participants, which will maintain the same planned statistical power (85%). This revised sample size will allow us to detect the more precise effect sizes currently reported in the literature and will also make the study feasible to be completed on time, given the large impact of the COVID pandemic on our study.

[figure not shown]
Planned Analysis:

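### The path-analysis rule infers a direct effect of tDCS and exercise on CPM/TSPS by default, so random error in the mediators could support a false direct-effect claim

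*Combined protocol and SAP*

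**What the plan says.** After the primary and secondary mixed models, Section VIII (Planned Analysis) adds a path analysis of CPM and TSPS. It asks whether changes under the combined intervention are "related to direct effects versus indirect effects through improvements in secondary outcomes", and proposes that a direct effect "can be inferred if the treatment effect cannot be explained by changes in psychological or functional outcomes".

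The visible text does not list the mediators or say which visits supply them. It gives no estimate, test or interval for either path. It does not say whether an unexplained effect means a non-significant indirect path or a significant residual effect. There is no power statement for this analysis and no provision for measurement error in the mediators. The sensitivity analyses named in that section concern missing data.

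The visit description places pain, quality of life, CPM and TSPS together at visits 11 and 17, and pain with CPM and TSPS at visits 6 and 14. Section VII describes the FIQ-R and BDI as given at the start of the study and at follow-up. Sub-aim 3 (Section II) looks at the same variables from the other side: "We hypothesize that changes in TSPS and CPM will be correlated with these pain outcomes".

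**The concern.** The rule turns a failure to account for an effect into positive evidence of a direct neurophysiological action. A measured mediator can fail to account for an effect that runs through it for two ordinary reasons. It may be measured with error, as self-report scales are, or the indirect path may be estimated too imprecisely to be shown. An unmeasured mediator would give the same result. None of these is a direct effect.

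A separate difficulty is direction. The path model places clinical change upstream of CPM/TSPS. If CPM/TSPS change drives pain instead, data from the same visit can show mediation that is not there.

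The protocol describes the trial as mechanistic, and this rule is what would license its statement on direct versus indirect action.

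**Working it through.** **1. The plan's own sample size.** Inputs from Section VIII: "using the smallest reported effect size (0.90) using the t-test calculation for the difference between two independent means"; "We assumed a type I error of 5% (alpha), and a type 2 error of 15% (beta"); two-sided tests; 20% dropout.

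- n per arm = 2 x (1.960 + 1.036)² / 0.90² = 22.2, so 23.
- 23 / 0.80 = 28.75, so 29 per arm; 29 x 4 = 116.

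This matches "we need a total of 116 participants (29 in each group) to achieve 85% power (as planned before"). With 23 evaluable per arm, exact t-test power at 0.90 SD is 84.7%. That is power for the total effect only.

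**2. Model for the check.** Two arms (combined and control), 23 per arm, T = 0 or 1, 20,000 simulated trials per scenario.

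- True mediator: M = aT + noise with SD 1.
- Outcome: Y = bM + noise, scaled so that Y has within-arm SD 1. There is no direct term, so the true direct effect is 0.
- Observed mediator: M plus random error, with reliability ρ.
- Full mediation at the design effect requires ab = 0.90. Three splits were used: 1.8 x 0.5, 1.5 x 0.6 and 1.2 x 0.75.

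The documents give neither the path sizes nor ρ. Both are assumptions, shown as ranges.

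**3. Reading A: a significant residual effect counts as direct.** The within-arm slope of Y on the observed mediator is bρ. The estimated indirect effect is therefore abρ = 0.90ρ, and the apparent direct effect is 0.90 - 0.90ρ = 0.90 x (1 - ρ).

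| Assumed reliability | Apparent direct effect (truth 0) | Significant in |
|---|---|---|
| 1.0 | 0 | 5% |
| 0.8 | 0.90 x 0.2 = 0.18 SD | 8-11% |
| 0.7 | 0.90 x 0.3 = 0.27 SD | 12-18% |
| 0.6 | 0.90 x 0.4 = 0.36 SD | 19-27% |

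The bias does not depend on sample size. At 29 per arm it is unchanged and is declared significant somewhat more often.

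**4. Reading B: a significant total effect with a non-significant indirect path counts as direct.** The indirect path was tested by joint significance of its two legs. Under full mediation this combination occurs in about 0.2-5% of trials with a perfect mediator and 3-15% at reliability 0.7.

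**5. Partial mediation.** If half of the 0.90 SD is mediated, power for the indirect path is 70-80% (52-58% at reliability 0.7). If about 30% is mediated, it is 36-44% (23-27%). A real indirect part is often missed here. A direct effect also exists, however, so calling the effect direct is incomplete rather than false.

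**6. Reverse direction.** Let treatment shift CPM by 0.90 SD and let CPM drive the clinical variable, with within-arm correlation r. The path model then estimates the direct effect as 0.90 x (1 - r²).

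| r | Estimated direct effect (truth 0.90) | Spurious indirect path significant in |
|---|---|---|
| 0.3 | 0.82 SD | 7% |
| 0.5 | 0.68 SD | 30% |
| 0.7 | 0.46 SD | 55% |

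The error here is false mediation and an understated direct effect.

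**The case against.** The best defence is that the analysis is supplementary and tentatively worded, and that the main mechanistic result rests on the randomised comparison of CPM and TSPS. That is right and limits the importance of the point. The cited path-analysis references and the nearby figures are also unavailable, so missing safeguards can be asserted only for the visible text.

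A second defence is that ordinary practice would require a residual effect after adjustment for the mediators (reading A), under which low power alone creates no false direct effect. This also stands. But mediator error still biases the residual under that reading, and the text does not choose between readings.

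Four stronger readings are tempting and are not supported:

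- *That low power would produce a false direct-effect claim in a large share of trials.* With a mediator shift of 0.6-0.9 SD and correlation 0.5, the indirect path is missed in 20-52% of trials (41-69% at reliability 0.7). But the total effect there is only 0.30-0.45 SD (0.6 x 0.5 to 0.9 x 0.5) and is significant in only 17-32% of trials. The rule needs a treatment effect to explain. Both conditions hold in about 3-5% of trials, or 8-10% at reliability 0.7.
- *That reverse causation manufactures a direct effect.* Step 6 shows that it hides one.
- *That Sub-aim 3 formally contradicts the path model.* It speaks mainly of association and correlation, which have no direction. Its use of baseline CPM/TSPS as predictors is a separate prognostic question.
- *That earlier measurements exist for every mediator.* Visits 6 and 14 list only pain as a clinical outcome, and the visible text does not confirm mid-treatment FIQ-R or BDI.

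**Conclusion.** The point holds in a limited form. The rule infers a mechanism by default, its criterion is undefined, and it could support a false direct-effect claim. Mediator error is the best-supported route: under full mediation at the design effect, a spurious direct effect of 0.18-0.36 SD, significant in roughly 8-27% of trials against 5%. If the rule turns on a non-significant indirect path, the false claim arises in about 0.2-5% of trials with a perfect mediator and 3-15% at reliability 0.7. Separately, same-visit data could show spurious mediation if CPM/TSPS drives pain.

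These sizes rest on a single mediator, 23 evaluable per arm, and assumed reliabilities and path sizes. A reader might infer that the trial's main conclusion is at risk. It is not: the randomised primary comparison does not use this rule. The change should be made, but the trial does not depend on it.

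**What to change.** - Delete the inference rule from the path-analysis paragraph.
- Report direct and indirect effects with bootstrap 95% confidence intervals, adjusted for baseline mediator and baseline outcome. These intervals express sampling error and do not remove bias from mediator error, so the next item is needed as well.
- State that no direct-effect claim will be made from a non-significant or incomplete indirect path.
- Label the path analysis exploratory.
- Where the schedule collects the mediator before visit 17 (pain at visits 6, 11 and 14; quality of life at visit 11), use the earlier measurement with the visit-17 CPM/TSPS outcome, and fit the reverse ordering as a sensitivity analysis.
- For instruments collected only at the start and at follow-up, state that direction cannot be established.

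The cost is a change of wording and modest extra analysis, with no new data collection. The downside is a more cautious mechanistic statement.
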